5.4.4.1 Hepatic Safety

Liver-associated enzymes and TB will be summarized by the value and change from baseline in the value, by treatment group and visit. In addition, the number and percent of patients with abnormal values for ALT ($> 3 \times \text{ULN}$, $> 5 \times \text{ULN}$), AST ($> 3 \times \text{ULN}$, $> 5 \times \text{ULN}$, and TB ($> 2 \times \text{ULN}$)) will be summarized. These summaries of patients with abnormal values will be performed overall safety population; by normal baseline; and by abnormal baseline for each of ALT, AST and TB. Hy's law criteria ($> 3 \times \text{ULN}$ for either ALT or AST, with accompanying TB $> 2 \times \text{ULN}$) will also be applied to the data; any potential Hy's law cases will be listed separately. Note: In the case of patients with Gilbert's disease, TB will be fractionated and the determination of $2 \times \text{ULN}$ will be based upon direct (conjugated) bilirubin.

5.4.4.2 Musculoskeletal Safety

CK levels will be summarized by the value and change from baseline in the value, by treatment group and visit as well as baseline eGFR category. In addition, the number and percent of patients with abnormal CK values ($> 5 \times \text{ULN}$, $> 10 \times \text{ULN}$) will be summarized for overall safety population. These summaries of patients with abnormal CK will be performed overall, normal baseline CK, and abnormal baseline CK.

5.4.4.3 Diabetes and Glycemia

For fasting serum glucose, a shift table from baseline with the number and percent of patients will be categorized as below:

Fasting glucose: $\geq 126 \text{ mg/dL}$; $100-125 \text{ mg/dL}$, and $< 100 \text{ mg/dL}$. These tables will be summarized by history of Diabetes.

Descriptive summary for fasting serum glucose will be provided by history of diabetics and treatment group at each scheduled visit.

5.4.4.4 Renal Safety

Baseline eGFR will be summarized by treatment group for actual value and for baseline eGFR categories. Shift tables of eGFR category from baseline over the study, will be provided by treatment group. Shift tables of urine protein (negative/positive) from baseline over the study, will be provided by treatment group. Values of CK over the study will be summarized by treatment group and by baseline eGFR category.

5.4.5 Physical Examinations (PEs)

Listings of PE data will include only those records where the body system at the baseline PE was normal, but the body system at a post-baseline PE was marked as 'Change from previous exam, clinically significant.' Only changes from baseline physical examination findings that meet the definition of an AE will be recorded on the AE page of the eCRF and will be summarized with other AEs.

5.4.6 Vital Signs

Actual values and changes from baseline in vital signs (SBP, DBP, heart rate, weight) will be summarized using descriptive statistics by treatment group and post-baseline time point on the observed values.

Vital signs data will be listed for each patient, with increases from baseline of >15 mmHg in systolic or diastolic blood pressure flagged.

For vital signs, observed values and changes from baseline will be summarized for all post-baseline study visits.

5.4.7 Electrocardiogram (ECG)

Shift tables for ECG data from baseline to end-of-study will be provided by treatment group. The data will be categorized as 'Normal'; 'Abnormal, not clinically significant'; and 'Abnormal, clinically significant.' Baseline is defined as the last value prior to the first dose of study medication. Listings of ECG data will include only those records where the baseline ECG was either 'Normal' or 'Abnormal, not clinically significant', but the end-of-study ECG was marked as 'Abnormal, clinically significant'.

6 Reference

2. World Health Organization (WHO) Fact Sheet No 317 Updated January 2015.
3. Robinson JG. Management of Familial Hypercholesterolemia: A Review of the recommendations from the National Lipid Association Expert Panel on Familial Hypercholesterolemia. J Managed Care Pharm. 2013;19(2):139-49.
5. ICH Topic E3: Structure and Content of Clinical Study Reports (CPMP/ICH/137/95- adopted December 1995).
6. ICH Topic E9: Statistical Principles for Clinical Trials (CPMP/ICH/363/96 – adopted March 1998).
7. Brendan M.Everett, Tobias Kurth, Julie E.Buring, Paul M.Ridker. "The Relative Strength of C-Reactive Protein and Lipid Levels as Determinants of Ischemic Stroke Compared With Coronary Heart Disease in Women." Journal of the American College of Cardiology (2006), Volume 48, Issue 11, Pages 2235-2242.

7 Appendices

Appendix 1: Schedule of Events (Patient Visit Schedule)

Visit	S1 ¹	T1	T2	T3	T4 ²
Week	-2	0	4	8	12/EOS
Procedure	Day -16 to -5	Day 1	Day 29 ± 5	Day 57 ± 5	Day 85 ± 5
Informed Consent	X				
Enrollment Criteria	X	X			
Demographics	X				
Medical History	X				
Concomitant\Prohibited Medications	X	X	X	X	X
Adverse Event Recording	X	X	X	X	X
Physical Exam		X			X
Weight ³	X	X ³	X	X	X
Height/BMI	X				
12-Lead ECG ⁴		X			X
Vital Signs ⁵	X	X	X	X	X
Serology ⁶	X				
Serum Pregnancy/FSH ⁷	X				
Urine Pregnancy		X			
TSH	X				
Clinical Safety Labs ⁸	X	X	X	X	X
Basic Fasting Lipids ⁹	X	X	X	X	X
Special Fasting Lipids and Other Biomarkers ¹⁰		X			X
HbA _{1C}	X				
Plasma Trough Study Drug			X	X	X
Randomization		X			
Double Blind Drug Dispensing		X	X	X	
Drug Return			X	X	X

¹ An optional visit approximately 10 days later MAY be completed if patient fails to meet specified entry criteria. If this optional visit is completed, the repeat value will be used to determine eligibility.

² All procedures will be completed at end of study or early termination.

³ Body weight will be measured in the morning while fasting, using consistent scales, after voiding, and without shoes and outerwear (e.g., coats).

⁴ Single 12-lead ECG will be collected prior to any blood sample collection.

⁵ Vital signs will include SBP, DBP, and HR, and will be collected prior to any blood sample collection. Patient will rest for 5 minutes prior to assessments.

⁶ Serology for Hep B antigen, Hep C antibody.

⁷ FSH completed in appropriate postmenopausal women only; pregnancy test completed in non-postmenopausal women only.

⁸ Clinical safety labs include hematology, blood chemistry, and urinalysis. Coagulation panel only if receiving anticoagulants that in the investigator's judgement requires monitoring (then test at T1 and repeat 3-5 days after starting IMP).

⁹ Basic fasting lipids include total cholesterol, calculated LDL-C, HDL-C, non-HDL-C, and triglycerides.

¹⁰Includes apoB and hs-CRP.

Appendix 2: AESI (Adverse Event of Special Interest)

AESI Category	Associated MedDRA Preferred Terms
Creatine kinase elevations	Blood creatine phosphokinase abnormal
Creatine kinase elevations	Blood creatine phosphokinase increased
Creatine kinase elevations	Blood creatine phosphokinase MM abnormal
Creatine kinase elevations	Blood creatine phosphokinase MM increased
New onset or worsening diabetes mellitus	Blood glucose abnormal
New onset or worsening diabetes mellitus	Blood glucose increased
New onset or worsening diabetes mellitus	Diabetes mellitus
New onset or worsening diabetes mellitus	Diabetes mellitus inadequate control
New onset or worsening diabetes mellitus	Diabetic ketoacidosis
New onset or worsening diabetes mellitus	Glucose tolerance impaired
New onset or worsening diabetes mellitus	Glucose urine present
New onset or worsening diabetes mellitus	Glycosuria
New onset or worsening diabetes mellitus	Glycosylated haemoglobin increased
New onset or worsening diabetes mellitus	Hyperglycaemia
New onset or worsening diabetes mellitus	Impaired fasting glucose
New onset or worsening diabetes mellitus	Ketoacidosis
New onset or worsening diabetes mellitus	Ketosuria
New onset or worsening diabetes mellitus	Ketosis
New onset or worsening diabetes mellitus	Type 2 diabetes mellitus
New onset or worsening diabetes mellitus	Urine ketone body present
Hepatic enzyme elevations	Alanine aminotransferase abnormal
Hepatic enzyme elevations	Alanine aminotransferase increased
Hepatic enzyme elevations	Aspartate aminotransferase abnormal
Hepatic enzyme elevations	Aspartate aminotransferase increased
Hepatic enzyme elevations	Blood bilirubin abnormal
Hepatic enzyme elevations	Blood bilirubin increased
Hepatic enzyme elevations	Hepatic enzyme abnormal
Hepatic enzyme elevations	Hepatic enzyme increased
Hepatic enzyme elevations	Hypertransaminaseaemia
Hepatic enzyme elevations	Liver function test abnormal
Hepatic enzyme elevations	Liver function test increased
Hepatic enzyme elevations	Transaminases abnormal
Hepatic enzyme elevations	Transaminases increased
Hypoglycemia	Blood glucose abnormal
Hypoglycemia	Blood glucose decreased
Hypoglycemia	Hypoglycaemia
Hypoglycemia	Hypoglycaemic coma
Hypoglycemia	Hypoglycaemic encephalopathy

AESI Category	Associated MedDRA Preferred Terms
Hypoglycemia	Hypoglycaemic seizure
Hypoglycemia	Shock hypoglycaemic
Metabolic acidosis	Metabolic acidosis
Muscular disorders	Muscular weakness
Muscular disorders	Muscle necrosis
Muscular disorders	Muscle spasms
Muscular disorders	Myalgia
Muscular disorders	Myoglobin blood increased
Muscular disorders	Myoglobin blood present
Muscular disorders	Myoglobin urine present
Muscular disorders	Myoglobinaemia
Muscular disorders	Myoglininuria
Muscular disorders	Myopathy
Muscular disorders	Myopathy toxic
Muscular disorders	Necrotizing myositis
Muscular disorders	Pain in extremity
Muscular disorders	Rhabdomyolysis
Neurocognitive disorder	Amnesia
Neurocognitive disorder	Cognitive disorder
Neurocognitive disorder	Confusional state
Neurocognitive disorder	Disorientation
Neurocognitive disorder	Memory impairment
Neurocognitive disorder	Mental status changes
Renal disorders	Acute kidney injury
Renal disorders	Acute prerenal failure
Renal disorders	Blood creatinine abnormal
Renal disorders	Blood creatinine increased
Renal disorders	Blood urea abnormal
Renal disorders	Blood urea increased
Renal disorders	Blood urea nitrogen/Creatinine ratio increased
Renal disorders	Creatinine renal clearance abnormal
Renal disorders	Creatinine renal clearance decreased
Renal disorders	Glomerular filtration rate abnormal
Renal disorders	Glomerular filtration rate decreased
Renal disorders	Oliguria
Renal disorders	Prerenal failure
Renal disorders	Renal failure
Renal disorders	Renal function test abnormal
Renal disorders	Renal impairment
Gout	Gout

Addendum to Statistical Analysis Plan

Title: A Randomized, Double-Blind, Parallel Group Study to Evaluate the Efficacy and Safety of Bempedoic Acid 180 mg + Ezetimibe 10 mg Fixed Dose Combination Compared to Bempedoic Acid, Ezetimibe, and Placebo Alone in Patients Treated with Maximally Tolerated Statin Therapy.

Protocol: ETC-1002FDC-053

Clinical Phase: 3

Product: ETC-1002FDC

Date: Dec 24, 2018

Addendum to the Statistical Analysis Plan for Study 1002FDC-053

An Ad-hoc Sensitivity Analysis

Esperion completed the planned analysis as described in Study 1002FDC-053 SAP for all data collected in the study. During an in-depth review of the data, after unblinding, a data issue was identified that involved three sites. A formal investigation to assess the root cause of the data issue was launched. After review of the investigative results, the conclusion led us to question the data collected at three sites [REDACTED]

[REDACTED]

[REDACTED]

[REDACTED]

To answer the question and ensure the integrity of the data and related analysis and quality, we propose to conduct sensitivity analysis. The focus of the sensitivity analysis is to examine if the data issue impacts the efficacy and safety results of the trial. We will repeat selected key analyses after excluding all 81 patients from these 3 sites, [REDACTED] and [REDACTED]

After excluding patients from these 3 sites [REDACTED], we will provide tables for disposition and demographics. We will repeat the statistical analyses for:

1. The co-primary efficacy endpoints, which consist of three comparisons of the percent change from baseline to Week 12 in LDL-C: bempedoic acid-ezetimibe fixed dose combination (FDC) vs. placebo, FDC vs. ezetimibe, and FDC vs. bempedoic acid;
2. Key secondary efficacy endpoints which include the percent change from baseline to Week 12 in non-HDL-C, TC, apoB, and hsCRP;
3. Overview of treatment emergent adverse events; and
4. Laboratory parameter of interest including ALT and AST abnormalities. The clinical relevance and statistical significance for the results will be re-evaluated for the primary and key secondary endpoints.

The safety profile will also be reviewed during the sensitivity analysis. The list of tables for sensitivity analysis is provided in

Table 1.

Table 1. List of Tables for Study 1002FDC-053 Sensitivity Analysis.

T14.1.1.1	Patient Disposition
T14.1.2.1	Demographic and Baseline Characteristics - Safety Population
T14.1.2.2	Demographic and Baseline Characteristics - Full Analysis Set
T14.2.1.1.1	Primary Analysis: Percent Change from Baseline in Low-density Lipoprotein Cholesterol (LDL-C) at Week 12 (Multiple Imputation (MI)) Full Analysis Set
T14.2.1.1.3	Sensitivity Analysis: Percent Change from Baseline in Low-density Lipoprotein Cholesterol (LDL-C) at Week 12 (Observed Data) Treatment Completer Analysis Set
T14.2.1.2.1	Statistical Analysis of Percent Change from Baseline in High-sensitivity C-reactive Protein (hsCRP) at Week 12 via Non-parametric Approach (Observed Data) Full Analysis Set
T14.2.1.3.1	Statistical Analysis of Percent Change from Baseline in Non-High-density Lipoprotein Cholesterol (Non-HDL-C) at Week 12 (Multiple Imputation (MI)) Full Analysis Set
T14.2.1.4.1	Statistical Analysis of Percent Change from Baseline in Apolipoprotein B (apo-B) at Week 12 (Multiple Imputation (MI)) Full Analysis Set
T14.2.1.5.1	Statistical Analysis of Percent Change from Baseline in Total Cholesterol at Week 12 (Multiple Imputation (MI)) Full Analysis Set
T14.2.2.1	Low-density Lipoprotein Cholesterol (LDL-C) Values and Changes and Percent Changes from Baseline (Conventional Unit) - Full Analysis Set
T14.2.7.1	Summary for Bempedoic Acid Plasma Concentrations by Visit - PK Analysis Set
T14.2.7.2	Summary for Ezetimibe Plasma Concentrations by Visit - PK Analysis Set
T14.3.1.1.1	Overview of Treatment-emergent Adverse Events - Safety Population

T14.3.1.2.1	Treatment-emergent Adverse Events (TEAEs) by System Organ Class and Preferred Term - Safety Population
T14.3.1.2.2	Treatment-emergent Serious Adverse Events (TE SAEs) by System Organ Class and Preferred Term - Safety Population
T14.3.1.2.3	Treatment-emergent Adverse Events (TEAEs) Resulting in Withdrawal of IMP by System Organ Class and Preferred Term - Safety Population
T14.3.1.2.5	Treatment-emergent Adverse Events of Special Interest (AESIs) by System Organ Class and Preferred Term - Safety Population
T14.3.1.4.1	Study-Drug Related Treatment-emergent Adverse Events (TEAEs) by System Organ Class and Preferred Term - Safety Population
T14.3.5.1a	Laboratory Parameters of Interest: Laboratory Abnormalities - Safety Population
Subset of T14.3.4.1.1	Values, Change from Baseline and Percent Change from Baseline in Serum Chemistry Lab Values for uric acid, hemoglobin and creatinine – Safety Population

Addendum II to Statistical Analysis Plan

Title: A Randomized, Double-Blind, Parallel Group Study to Evaluate the Efficacy and Safety of Bempedoic Acid 180 mg + Ezetimibe 10 mg Fixed Dose Combination Compared to Bempedoic Acid, Ezetimibe, and Placebo Alone in Patients Treated with Maximally Tolerated Statin Therapy.

Protocol: ETC-1002FDC-053

Clinical Phase: 3

Product: ETC-1002FDC

Date: Dec 17, 2018

Addendum II to the Statistical Analysis Plan for Study 1002FDC-053

Post-hoc Analysis

Esperion completed the planned analyses as described in Study 1002FDC-053 SAP for all data collected in the study. After unblinding, some issues of clinical interest were identified. The following is the listing of the tables to address these issues.

Listing of Tables:

Table 17.2.1.1	Statin at Baseline by Anatomic Therapeutic Chemical Class and Preferred Term Full Analysis Set
Table 17.3.1.1	Post-Randomization Abnormal Liver Function Summary Safety Population
Table 17.4.1.1.1	Laboratory Parameters of Interest: Laboratory Abnormalities Subjects on High Intensity Statin at Baseline Safety Population
Table 17.4.1.1.2	Laboratory Parameters of Interest: Laboratory Abnormalities Subjects on Other Intensity Statin at Baseline Safety Population
Table 17.4.1.1.3	Laboratory Parameters of Interest: Laboratory Abnormalities Subjects on No Statin at Baseline Safety Population
Table 17.5.1.1.1	Percent Change from Baseline in Low-density Lipoprotein Cholesterol (LDL-C) at Week 12 by Calculated Baseline Statin Intensity (Observed Data) Full Analysis Set
Table 17.5.1.1.2	Percent Change from Baseline in Low-density Lipoprotein Cholesterol (LDL-C) at Week 12 by Calculated Baseline Statin Intensity (Observed Data) Treatment Completer Analysis Set

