4.2.1. Mechanism of Action

Bempedoic acid is a first-in-class small molecule that decreases cholesterol synthesis in the liver. Bempedoic acid is a prodrug that requires coenzyme A (CoA) activation by very long-chain acyl-CoA synthetase 1 (ACSVL1) to ETC-1002-CoA. ETC-1002-CoA inhibits ACL, an enzyme upstream of HMG-CoA reductase in the cholesterol biosynthesis pathway. Like statins, BA decreases liver cholesterol synthesis, which results in increased LDL receptor activity and LDL particle clearance from the blood.

[figure not shown]
Both ETC-1002-CoA (via ACL inhibition) and statins (via HMG-CoA reductase inhibition) inhibit cholesterol synthesis in the liver, but an important differentiating feature is that unlike statins, BA is inactive in skeletal muscle. This is consistent with the absence of ACSVL1 (the synthetase required to activate BA to ETC-1002-CoA and inhibit ACL) expression in muscle tissue. Evidence suggests that muscle-related adverse effects associated with statin use is a result of HMG-CoA reductase inhibition directly in skeletal muscle leading to a reduction of several downstream biological intermediates within the cholesterol synthesis pathway important for muscle cell function. Since BA is not activated to ETC-1002-CoA and does not inhibit cholesterol synthesis in muscle tissue, it is anticipated that negative muscle-related adverse effects associated with statin use may be avoided by use of BA. The long-term safety of BA and its metabolites regarding human skeletal muscle is not yet established.

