13.1.3. Reporting for Adverse Events

All AEs occurring during the course of the study (starting from signing informed consent to study completion or discontinuation) will be collected on the AE eCRF. Patients should be instructed to report any AE that they experience to the Investigator through 30 days following study completion or discontinuation. Beginning with Visit S1 (Week -2), Investigators should make an assessment for AEs at each visit and record the event on the appropriate AE eCRF. Any SAE that occurs from the time of signing informed consent through 30 days following study completion should be reported to the Sponsor per [Section 13.2.4](#).

Wherever possible, a specific disease or syndrome rather than individual associated signs and symptoms should be identified by the Investigator and recorded on the eCRF. However, if an observed or reported sign or symptom is not considered a component of a specific disease or syndrome by the Investigator, it should be recorded as a separate AE on the eCRF. Additionally,

the condition that led to a medical or surgical procedure (e.g., surgery, endoscopy, tooth extraction, transfusion) should be recorded as an AE, not the procedure. Any medical condition already present at screening or baseline should not be reported as an AE unless the medical condition or signs or symptoms present at baseline changes in severity or seriousness at any time during the study. In this case, it should be reported as an AE.

Clinically significant abnormal laboratory or other examination (e.g., ECG) findings that are detected during the study or are present at baseline and significantly worsen during the study should be reported as AEs. The Investigator will exercise his or her medical and scientific judgment in deciding whether an abnormal laboratory finding or other abnormal assessment is clinically significant. Significant abnormal laboratory values occurring during the clinical study will be followed until repeat tests return to normal, stabilize, or are no longer clinically significant. Any abnormal test that is determined to be an error does not require reporting as an AE.

Each AE is to be evaluated for duration, severity, seriousness, and causal relationship to the investigational drug. For each AE, the following information will be recorded:

- Description of the event (e.g., headache);
- Date of onset;
- Date of resolution (or that the event is continuing);
- Action taken as a result of the event;

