5.4.2 Adverse Events of Special Interest (AESIs)

AESIs include hepatic disorders (including increase from baseline in hepatic aminotransferases), musculoskeletal events (AE and CK evaluation), new onset diabetes/hyperglycemia, renal events, metabolic acidosis and/or hypoglycemia, and neurocognitive/neurologic events. The list of AESI terms is pre-defined by the Esperion and is included in Appendix 2.

- AESIs of muscle related symptoms will be summarized by treatment group. CK levels will be summarized by the value and change from baseline in the value, by treatment group and visit. In addition, the number and percent of patients with abnormal CK ($> 5 \times \text{ULN}$, $> 10 \times \text{ULN}$) values will be summarized. These summaries of patients with abnormal CK will be performed overall; by normal baseline CK; and by abnormal baseline CK.
- Cases of new onset of diabetes will be recorded as AEs and will be summarized using the appropriate SOC. These events will be summarized by severity, and relationship to study drug for each treatment group. Fasting glucose will be summarized at scheduled time point by history of diabetics.
- Neurocognitive events will be evaluated by routine safety monitoring of PE findings and AEs. Neurocognitive events will be identified using pre-specified MedDRA terms and will be summarized by SOC, severity, and relationship to IMP for each treatment group

AESI will be presented in a listing and summarized by AESI category, SOC, PT and treatment group.

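### The muscle AESI term list in SAP Appendix 2 includes necrotizing myositis but not plain myositis, so a case coded to the general term would be missing from the term-based muscle AESI tables

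*SAP*

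**What the plan says.** SAP 5.4.2 counts among the AESIs "musculoskeletal events (AE and CK evaluation"), says that the sponsor fixed the term list in advance, and refers to Appendix 2 for it. Muscle AESIs are then summarized by treatment group.

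Appendix 2 has 14 entries under Muscular disorders. They include "Rhabdomyolysis", "Myopathy toxic", "Myoglobin urine present" and "Necrotizing myositis". One entry is printed as "Myoglininuria". Four CK terms form a separate category, Creatine kinase elevations.

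On how events reach the database, Protocol 13.1.3 says: "Wherever possible, a specific disease or syndrome rather than individual associated signs and symptoms should be identified by the Investigator". The same section asks for a cluster of signs with a single cause to be reported as one AE.

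**The concern.** A list that names a rare, qualified form of a diagnosis would normally also name the general form. This one does not, and neither document explains why. Appendix 2 decides which preferred terms count, so an event coded to plain *Myositis* is not a muscle AESI.

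The recording rule in Protocol 13.1.3 makes this more than a formality. Take a patient with muscle pain and a raised CK. Reported as symptoms and signs, the patient could be counted under *Myalgia* and under the CK category. Reported as a single diagnosis of myositis, the same patient could be counted under neither.

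At stake is the completeness of a descriptive safety category that the sponsor has reason to present well. Protocol 4.2.1 states that "it is anticipated that negative muscle-related adverse effects associated with statin use may be avoided by use of BA", and adds that long-term skeletal-muscle safety is not yet established. With about 100 patients per active arm, one case can decide whether a category shows zero or not.

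**Working it through.** The plan states no figure to reproduce; the check is mainly a comparison of terms.

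**1. The list.** The Muscular disorders entries in SAP Appendix 2 are: Muscular weakness, Muscle necrosis, Muscle spasms, Myalgia, Myoglobin blood increased, Myoglobin blood present, Myoglobin urine present, Myoglobinaemia, Myoglininuria, Myopathy, Myopathy toxic, Necrotizing myositis, Pain in extremity, Rhabdomyolysis. That is 14.

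**2. Matching against the list.**

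| Term sought | Exact matches | Related entries |
|---|---|---|
| Myositis | 0 | 1 (Necrotizing myositis) |
| Myoglobinuria | 0 | 1 entry printed as Myoglininuria; 4 other myoglobin entries, including Myoglobin urine present |

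Five entries name a diagnosed muscle injury or disease: Muscle necrosis, Myopathy, Myopathy toxic, Necrotizing myositis and Rhabdomyolysis. The gap is therefore the single general term.

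**3. Outputs that use the list.** These are the AESI line of the TEAE overview, the AESI and serious-AESI tables and the AESI listing (SAP 5.4.1 and 5.4.2), the subgroup AESI tables (SAP 5.4.3), and table T14.3.1.2.5 in the first SAP addendum.

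**4. Outputs that would still show the case.**
- TEAEs by SOC and preferred term, and by preferred-term frequency; also the related, serious and withdrawal tables where they apply (SAP 5.4.1).
- CK above 5 and above 10 times ULN from laboratory values, which SAP 5.4.4 places within the AESI evaluation and SAP 5.4.4.2 repeats by baseline CK.
- A smaller CK rise appears only in the value summaries and the counts outside the normal range. Under Protocol 12.1.6.4, a laboratory abnormality already tied to an AE does not normally become an AE of its own, so it need not reach the CK AESI terms.

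**5. Scale, by assumption only.** The documents give no incidence for plain myositis. If a proportion p of patients had an event coded to it, the chance of at least one in n patients is 1 − (1 − p)^n.

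| Assumed p | Expected in 100 (100 × p) | At least one in 100 | At least one in 350 |
|---|---|---|---|
| 0.1% | 0.1 | 1 − 0.999^100 = 9.5% | 1 − 0.999^350 = 29.5% |
| 0.5% | 0.5 | 1 − 0.995^100 = 39.4% | 1 − 0.995^350 = 82.7% |
| 1% | 1.0 | 1 − 0.99^100 = 63.4% | 1 − 0.99^350 = 97.0% |

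If one such case were the only muscle event in an active arm, the category would read 0/100 (exact 95% interval 0 to 3.62%) instead of 1/100 (0.03% to 5.45%). The two intervals overlap almost entirely.

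**The case against.** The strongest reply is that the list already covers diagnosed muscle injury. That largely stands. Rhabdomyolysis, myopathy, toxic myopathy, muscle necrosis and necrotizing myositis are all listed, so a reader who infers that diagnosed muscle injury as a whole drops out would be wrong.

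An omitted case is also not hidden. It stays in the general TEAE tables and listings, and a marked CK rise is counted within the AESI evaluation however the AE is coded. This stands and limits the consequence.

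Nothing in Protocol 13.1.3 says that muscle pain with a CK rise becomes myositis rather than myopathy or rhabdomyolysis, both of which are listed. This stands too: the rule makes the gap reachable, but does not show that cases fall into it.

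The odd spelling is weak evidence by itself. It may come from typing or from reading the PDF, and the SAP does not say that AESIs are flagged by matching the printed text; AEs are MedDRA-coded. It supports a check of the list, not a claim that cases are lost.

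A reader might also ask for general musculoskeletal pain and discomfort terms, because SAP 5.4.2 says musculoskeletal. But Protocol 13.3 calls the category muscular, and SAP 5.4.2 goes on to speak of muscle-related symptoms. Leaving the wider terms out is a defensible choice of scope.

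None of this explains why the narrow form of myositis is listed and the general form is not.

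**Conclusion.** The point holds in a narrow form. Plain *Myositis* is missing from a pre-defined list that includes its qualified form, and an event coded to it would be left out of the term-based muscle AESI outputs. This assumes that AESIs are flagged strictly from Appendix 2, as SAP 5.4.2 implies, and that at least one case was coded to the general term.

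The size cannot be computed from the documents; the incidences in the working are assumptions. The number of cases is likely to be small, and no percentage shortfall in the muscle category can be supported.

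It might be inferred that the count tests a muscle advantage over statins. The documents do not support this: SAP 5.4 makes safety descriptive, Protocol 4.2.1 states an expectation only, and maximally tolerated statin is background therapy in every arm, with no randomized statin comparator. Efficacy conclusions are unaffected. This is a minor point that is cheap to correct.

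**What to change.** Add *Myositis* to Muscular disorders in Appendix 2, which takes the list from 14 to 15 entries, or document why it was left out. Check that every Appendix 2 entry, including the one with the doubtful spelling, resolves to a preferred term in the MedDRA version used for coding, and name that version beside the list.

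Both SAP addenda state that the planned analyses were completed and the data unblinded. The AESI tables made with the present list should therefore be kept, and the corrected-list tables and listing presented beside them as a labelled post hoc supplement.

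The cost is one added row, one term check and a re-run of existing programs. The downsides are that the muscle AESI percentage may rise slightly and that the supplement carries less weight than a pre-specified analysis.
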